#### *Additional biomarkers*

Additional biomarkers will include the modulation of hs-CRP as marker of inflammation, the evaluation of urinary cotinine as marker of tobacco exposure and investigation of the potential effect of aspirin according to its concentration, the measurement of urinary PGEM and LTE4 normalized to urinary creatinine concentration. Serum TXB2 will be determined as a measure of compliance. Results will be compared between the two treatment arms (aspirin and placebo).

### Tolerability

Aspirin tolerability will be evaluated.

## **8.3 Off-Agent Criteria**

Participants may stop taking study agent for the following reasons: completed the protocol-prescribed intervention, adverse event or serious adverse event, inadequate agent supply, noncompliance, concomitant medications, medical contraindication. Participants will continue to be followed, if possible, for safety reasons and in order to collect endpoint data according to the schedule of events. Subjects will not be replaced.

## **8.4 Off-Study Criteria**

Participants may go ‘off-study’ for the following reasons: the protocol intervention is completed, protocol violation, adverse event/serious adverse event, lost to follow-up, physician decision (i.e., non-compliance, concomitant medication, medical contraindication), participant withdrawal (i.e., withdraw consent), death, ineligibility or screening failure, disease progression or other reason.

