### 5.5 Concomitant Medications

Other NSAIDs or glucocorticosteroids should be avoided or limited. Any use of systemic or topic NSAIDs or glucocorticosteroids should be clearly documented (time, doses, routes, indications) and followed regularly.

If a participant requires pain relievers or antipyretics, the use of non-NSAIDs, e.g., acetaminophen, should be encouraged. It is not necessary to break the blind in most situations. A protonic pump inhibitor (PPI, omeprazole 20 mg/day tablet) will be added during the period of any NSAIDs or glucocorticosteroids treatment and will be stopped once NSAIDs or glucocorticosteroids are withdrawn.

Short courses of systemic NSAIDs or glucocorticosteroids (defined as up to 2 weeks at a time) are allowed. No more than 1 month total of off-protocol NSAIDs or glucocorticosteroids is allowed in a 6 months period. If it is anticipated that continuous NSAIDs or glucocorticosteroids will be needed or if more than 1 month of NSAIDs or glucocorticosteroids occurs during a 6 months period, the participant will stop study drug. However, since the participant will still undergo his/her yearly scan, they can still be assessed in an intent-to-treat analysis and thus do not come off the study. Non systemic glucocorticosteroids use is allowed without time restrictions.

All medications (prescription and over-the-counter), vitamin and mineral supplements, and/or herbs taken by the participant will be documented on the concomitant medication CRF and will include: 1) start and stop date, dose and route of administration, and indication. Medications taken for a procedure (e.g., biopsy) should also be included.

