### 5.6 Dose Modification

Subjects will be asked to maintain the full dose throughout the treatment period. However, should some toxicity appear, dose modification will be applied and recorded.

Toxicity will be evaluated at each visit using the most recent version of the NCI terminology criteria (CTCAE version 4.0.3, published 06/14/2010).

If grade 1 toxicity occurs, the patient will be maintained on full dose. Toxicity will be checked depending on clinical relevance.

In case of grade 2 toxicity or higher, the dose will be changed according to the potential relationship to study drug as listed in the table below.

Toxicity	Attribution to study drug				
Grade	Unrelated	Unlikely	Possible	Probable	Definite
1	C	C	C	C	C
2	C	C	S-R 	S-R 	S-R 
3	S-R 	S-R 	S-R 	W	W
4	S-R 	S-R 	W	W	W

C = Continue drug

S-R^0 = Stop drug until toxicity reaches grade 1 or lower, then restart drug at full dose (100 mg/day). If toxicity resumes, stop drug again until toxicity reaches grade 1 or lower, and then restart at alternate day and maintain the reduced dose.

S-R^1 = Stop drug until toxicity reaches grade 1 or lower, then reduce drug by 50% (100 mg at alternate day) and maintain the reduced dose.

[figure not shown]
S-R^2 = Stop drug until toxicity reaches grade 1 or lower, then reduce drug by 50% (100 mg at alternate day) for 1 month. If toxicity is no more than grade 1, restart drug at full dose (100 mg/day). If toxicity resumes after reintroduction of full dose, stop drug again until toxicity reaches grade 1 or lower and then reduce drug by 50% (100 mg at alternate day) and maintain this dose. No further reductions will be permitted and patients with returning toxicities will be removed from the study.

W = Withdrawal

For dyspepsia and GERD management only, a PPI1) will be added.

In case of dyspepsia grade 1 (G1), PPI will be added for two weeks. If remission, PPI will be stopped. If symptom persists or recurs, it will be defined as  $\geq$  grade 2 (G2).

In case of dyspepsia  $\geq$  G2, the symptom will be managed as follows:

The clinical investigators of the study may be helped in their decisions by consultation of other specialists (Gastroenterologist).

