## 6.9 Blinding and Unblinding Methods

- Participants will be blinded to aspirin or placebo.
- The Statistician and the Study Pharmacist will not be blinded to Aspirin or placebo.
- All other Investigators will be blinded to Aspirin or placebo.
- The MDACC Data and Safety Monitoring Board will also be blinded unless unblinding is warranted (the reasons for unblinding are outlined below).
- All participants will take 1 tablet per day of aspirin/matching placebo.
- Study assignments will be unblinded to the Study Investigators and Site Coordinators after all of the data are collected and the study database has been locked. Unblinding will also occur if the participant’s physician deems that unblinding is necessary, such as in the case of unacceptable toxicity thought to be related to the study agent or progressive disease, or if the participant becomes pregnant.
- Unblinding will only take place after consultation with the NCI, DCP Task Order Monitor [name].
- If unblinding is indicated prior to the completion of the study, it will be conducted as follows:
  - The Site PI contacts the Protocol Chairman (the Protocol Principal Investigator) and requests the participant’s treatment status be unblinded.
  - The Protocol Chairman (the Protocol Principal Investigator) contacts the NCI, DCP Task Order Monitor (Medical Monitor) and requests the participant’s treatment status be unblinded. The Protocol Chairman then conveys the Task Order Monitor’s decision to the Site PI. The Site PI then proceeds with unblinding as written out below.
  - If the NCI Task Order Monitor cannot be reached and the participant requires emergency care, the Protocol Chairman (the Protocol Principal Investigator) may authorize the site PI to break the blind.
  - If the Site PI is unable to reach the Protocol Chairman and the participant requires emergency care, then the Site PI must proceed with unblinding as written out below.
  - The Site PI requests the participant’s treatment status be unblinded by the research pharmacist (or designated individual responsible for dispensing drug).
  - The Site PI officially takes the participant off-study.
  - The date and reason for breaking the blind must be submitted by the Site PI to the Protocol Chairman, [name], as soon as possible.
  - It is the responsibility of the Study Chairman to report the date and reason for breaking the blind to the **NCI Task Order Monitor**, [name], as soon as possible.

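### Sections 6.9 and 5.6 take participants off study after events for which 8.3 and 5.5 keep them in follow-up, so some obtainable month-12 CTs would be forgone

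*Combined protocol and SAP*

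**What the plan says.** Two sections keep participants in the trial after they stop drug.

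- Section 8.3 lists reasons for stopping agent, among them adverse events, noncompliance, concomitant medications and medical contraindication. It then says: "Participants will continue to be followed, if possible, for safety reasons and in order to collect endpoint data according to the schedule of events". It also says that subjects are not replaced.
- Section 5.5 covers participants who need more NSAID or steroid treatment than the protocol allows. They stop drug, but because the yearly scan still takes place "they can still be assessed in an intent-to-treat analysis and thus do not come off the study".

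Two sections require the opposite.

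- Section 6.9 sets out the steps for early unblinding. One step is unconditional: "The Site PI officially takes the participant off-study". Its examples of when to unblind are "such as in the case of unacceptable toxicity thought to be related to the study agent or progressive disease", "or if the participant becomes pregnant".
- Section 5.6, at the end of the S-R2 rule, says: "No further reductions will be permitted and patients with returning toxicities will be removed from the study".

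One section permits it. Section 8.4 says participants may go off study for a list of reasons that includes "adverse event/serious adverse event, lost to follow-up, physician decision (i.e., non-compliance, concomitant medication, medical contraindication".

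**The concern.** The primary endpoint is the change in the sum of longest diameters at 12 months. Section 13.9 confirms that repeat CT is planned only at baseline and one year. The month-3 and month-6 scans in the schedule of events are optional, and the Early Termination column has no CT. A participant taken off study before month 12 therefore has no planned post-baseline measurement of the primary endpoint.

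An intention-to-treat comparison needs the month-12 scan from participants who stopped drug as much as from those who continued. Sections 8.3 and 5.5 recognise this. If a site instead follows 6.9 or 5.6, a scan that could have been taken is given up, in part because of toxicity. Toxicity may differ between aspirin and placebo, so such losses need not be unrelated to arm. Section 13.4 (missing final CTs go into the failure group) and section 13.6 (multiple imputation above 5% missing) deal with scans already missing; neither recovers one.

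**Working it through.** No figure in the plan is at issue, so the check is a comparison of the rules, one event at a time.

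1. **Unblinding for drug-related toxicity.** If the participant stops agent for that toxicity, 8.3 applies, because an adverse event is one of its named reasons: follow-up continues for endpoint data. Section 6.9 sends the same person off study. This is a direct conflict, and the 6.9 step leaves no discretion.

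2. **Unblinding for progression or pregnancy.** Section 6.9 again requires off-study. Section 8.3 does not name progression. Pregnancy overlaps with 8.3 only through medical contraindication, and CT may then be inappropriate anyway. The conflict is not established for progression and is of little consequence for pregnancy.

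3. **Returning toxicity under S-R2.** The dose table assigns S-R2 to grade 3 or 4 events judged unrelated or unlikely to be related. The participant stops, takes half dose for a month, returns to full dose, has a recurrence, goes back to half dose for good, and then has toxicity return again. Section 5.6 says removal from the study. Section 8.3 would keep someone who stops agent for an adverse event in follow-up. This is a direct conflict, but it needs a long sequence of events.

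4. **Stopping agent without unblinding or S-R2.** Leaving completion aside, 8.3 names five reasons for stopping: adverse event, inadequate supply, noncompliance, concomitant medications and medical contraindication. Four of the five (all but supply) also appear in 8.4 as permitted reasons for going off study. For concomitant NSAIDs or steroids, 5.5 settles the matter in favour of staying on study. For the other three, 8.3 sets the default and 8.4 allows a departure from it. This is ambiguity; nothing in 8.4 compels an exit.

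5. **Which rule prevails.** No section says. A site can cite 6.9 or 5.6 for ending follow-up and 8.3 for continuing it.

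6. **What is lost.** Once a participant is off study, no text provides for the month-12 CT. Many participants would still have a yearly screening CT, but no text says it is used for the trial after off-study. Participants recruited outside a screening programme, whom section 4.1.3 allows, need not have one.

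**The case against.** The best defence has four parts.

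- **Section 8.4 is permissive.** It says participants may go off study, and its list also contains completion, death and screening failure. Section 6.8 requires everyone who signs consent to go off study formally, so 8.4 reads partly as a list of closing codes. This stands. A reader might infer that 8.4 itself forces participants out; it does not, and under 8.4 alone a site could follow everyone. The point therefore rests on 6.9 and 5.6.
- **The mandatory rules are narrow.** Section 6.9 says "Unblinding will only take place after consultation with the NCI, DCP Task Order Monitor", with exceptions for emergencies, so early unblinding should be uncommon. S-R2 needs repeated recurrence of events not attributed to drug. Since it sits in a dose-modification section, its removal sentence may have been meant as removal from drug. This stands as to frequency. It does not remove the conflict, and if off agent was meant, the text should say so.
- **Off study does not mean unscanned.** Screening participants have yearly CTs, and section 7.5 continues CT as needed. This stands in part: it shows that the scan is often obtainable, but no provision brings it into the trial's data.
- **Section 8.3 already settles it.** It governs participants who are off agent. Sections 6.9 and 5.6 move them to a different status, off study, to which 8.3 does not expressly apply.

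**Conclusion.** The conflict is in the text and is worth correcting, though its effect is probably small. It is firm for unblinding because of toxicity (6.9) and for returning toxicity under S-R2 (5.6). Section 8.4 contributes ambiguity only. The conclusion assumes that sites apply 6.9 and 5.6 literally and that being off study ends trial-directed CT; the documents do not say otherwise.

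Three stronger conclusions are tempting and not supported.

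- A reader might infer a measurable loss of power. The documents give no rate for early unblinding, S-R2 recurrence or discretionary exits, so any figure would describe dropout in general and not this wording.
- A reader might infer a biased treatment comparison. Exits related to toxicity make that possible, but neither its direction nor its size can be derived.
- A reader might add that off-study for ineligibility in 8.4 defeats section 13.8, which assesses response even in ineligible participants. The same section bases efficacy conclusions on eligible participants, so a scan lost for that reason need not affect them.

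**What to change.** - **Sections 6.9 and 5.6 (S-R2):** replace the off-study and removal wording with *off agent, with follow-up under section 8.3, including the month-12 CT and the month-13 contact, unless consent is withdrawn or CT is medically inappropriate (for example in pregnancy)*.
- **Section 8.4:** state that an adverse event, non-compliance, concomitant medication or medical contraindication alone leads to off-agent status under 8.3 and does not end endpoint follow-up.

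The stop and restart dose rules in 5.6 and the other off-study reasons in 8.4 can stay as they are.

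The cost is an amendment to the wording of three sections and a few extra contacts and CTs, most of which 8.3 already intends. Section 7.6 puts the average effective dose of a low-dose CT below 1.5 mSv; it gives no dose for standard CT, which some participants would have.

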MDACC launched its Lung Cancer Screening Program in 2011. To date, nearly 800 participants have been screened averaging approximately 20-30 screened participants per month. An additional resource for screening CTs is the active protocol entitled *“Biospecimen Banking and Biomarker Validation for Lung Cancer Early Detection in Cohort Receiving Low Dose Helical Computed Tomography Screening”* which has 194 participants currently enrolled. Although literature indicates the frequency of eligible lesions is approximately 30%, MDACC’s experience is slightly less at 10% (2-3 participants per month) identified by low dose screening CT scan. From this population, it is anticipated the Lung Cancer Screening program may enroll approx. 1 eligible participant per month after evaluation of other eligibility criteria. However, with the inclusion of lesions identified by diagnostic CT scan, MDACC’s large cancer survivor population offers a larger pool of potentially eligible participants undergoing CTs for surveillance.

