#### Baseline and Randomization:

- Signed informed consent.

- Collection of a blood samples (safety including  $\beta$ -HCG if applicable, biomarkers including TXB2 and biorepository), urine samples (biomarkers), physical exam and medical history including baseline symptoms; concomitant medications; confirmation of eligibility criteria
- Participants are randomized to receive either study agent or placebo and will be given a 7-month supply of drug or placebo (a kit containing 7 bottles of drug or placebo, with 30 tablets in each bottle, 1 tablet per day) together with a daily calendar.

Month 1 (+/- 1 weeks from randomization):

Phone contact in order to:

- record concomitant medications and record and evaluate adverse events;
- record self-reported compliance.

Month 3 (+/- 2 weeks from randomization):

Phone contact in order to:

- record concomitant medications and record and evaluate adverse events;
- record self-reported compliance.
- confirm date of the next schedule clinic visit and blood/urine tests
- CT scan if determined to be needed during multidisciplinary meetings

Participant will be asked to return used and unused boxes at the month 6 visit.

Month 6 (+/- 2 weeks from randomization):

- Participants will undergo physical exam, vital signs, weight, lab test (including  $\beta$ -HCG, if applicable) and biological sample collection (blood, urine) for biomarker measurement including TXB2.
- Concomitant medications will be recorded and adverse events will be recorded and evaluated.
- Compliance will be measured (subjects will be asked to return both used and unused bottles as well as calendar).
- CT scan if determined to be needed during multidisciplinary meetings

A 7-month supply of drug or placebo will be provided (a kit containing 7 bottles of drug or placebo, with 30 tablets in each bottle, 1 tablet per day).

Month 9 (+/- 2 weeks from randomization):

Phone contact in order to:

- confirm date of the next CT scan and month 12 clinic visit and ;
- record concomitant medications and record and evaluate adverse events;
- record self-reported compliance.

Month 12 (+/- 2 weeks from randomization):

- Participants will undergo physical exam, vital signs, weight, lab test and biological sample collection (blood and urine) for biomarker measurement including TXB2 and biorepository.
- Concomitant medications will be recorded and toxicity will be evaluated.

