## 13.4 Primary Objective, Endpoint(s), Analysis Plan

All randomized patients who received at least one dose will be included in the study analysis with an intent-to-treat approach. A secondary analysis will also be carried out after excluding non-compliers and subjects who will drop-out and who will refuse treatment after randomization.

Subject will be considered compliant if at least 80% of the drug has been taken.

Using a more conservative approach, patients who drop-out or have missing final CT scans will be considered in the failure group. Both the intent-to-treat and efficacy analyses will be conducted on a per subject basis. A two-sided paired t-test will be used to compare the average change in the dimension of sub-solid nodules in the aspirin group compared to the placebo group at 1 year.

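### A participant whose nodules progress before month 12 may be taken off study, and no sentence secures the month-12 CT that the primary endpoint needs; the effect is probably small

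*Combined protocol and SAP*

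**What the plan says.** - **Section 8.4 (off-study).** The list of reasons for which a participant may go off study ends with "death, ineligibility or screening failure, disease progression or other reason". The section does not mention any later CT.
- **Section 8.3 (off-agent).** Participants who stop study agent continue to be followed, if possible, for safety and "in order to collect endpoint data according to the schedule of events". Progression is not among the reasons listed before that sentence.
- **Section 6.9 (unblinding).** The examples of when a physician may judge unblinding necessary include "unacceptable toxicity thought to be related to the study agent or progressive disease". The steps that follow include "The Site PI officially takes the participant off-study".
- **Section 5.5 (NSAID or steroid use).** Participants who must stop study drug for this reason stay on study: "since the participant will still undergo his/her yearly scan, they can still be assessed in an intent-to-treat analysis".
- **Section 7.1 and the schedule table.** Months 3 and 6 carry "CT scan if determined to be needed during multidisciplinary meetings". The month-12 CT is planned for all. The Early Termination column has no CT.
- **Section 13.4.** For the analysis, "patients who drop-out or have missing final CT scans will be considered in the failure group".
- **Section 13.8.** Everyone who took at least one dose is to be assessed for response.

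**The concern.** The primary endpoint (8.1) is the person-level change in the sum of longest diameters at 12 months. Progression as defined in 8.2 is growth in that same quantity, or a new lesion. A new subsolid lesion that is persistent and at least 4 mm also enters the primary sum under 8.1. A participant who leaves for progression is therefore one whose month-12 sum would probably have risen. If aspirin works, more of these participants are on placebo. Losing them makes the placebo arm look better and shrinks the estimated effect.

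The analysis plan does not clearly repair such a loss. A failure group has no value in millimetres for a t-test on change. Multiple imputation (13.6) starts only above 5% missing, and nothing says that diameters from interim scans would enter it.

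**Working it through.** **1. The texts side by side.**

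| Situation | Status | Month-12 CT stated? |
|---|---|---|
| NSAID or steroid use (5.5) | stops drug, stays on study | yes |
| Listed off-agent reasons (8.3) | off agent | endpoint data collected if possible |
| Disease progression (8.4) | may go off study | no |
| Any unblinding (6.9) | taken off study | no |

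**2. When the scan can be lost.** Progression first seen on the month-12 CT costs nothing. Loss requires that progression is seen earlier, on an optional month-3 or month-6 CT or on a CT outside the trial schedule. The second route exists because MD Anderson's cancer survivor population, in the words of section 4.4, "offers a larger pool of potentially eligible participants undergoing CTs for surveillance".

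**3. The plan's own figure.** Section 13.3 gives 64 per arm, mean changes of -0.2 mm (placebo) and -1.0 mm (aspirin), SD 1.6 mm, two-sided alpha 0.05. The effect size is 0.8/1.6 = 0.5. The exact two-sample t-test needs 63.8 per arm, and 64 per arm gives power 0.801. The stated sample size reproduces.

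**4. Size of the loss.** Assumptions that are not in the documents: normally distributed changes; everyone scanned at month 6; progression means growth of at least 2 mm by then; every progressor leaves and is not imputed. The 2 mm figure is the minimum in 8.2. For a sum above 10 mm, 20% growth needs more than 2 mm, so applying 2 mm to everyone is generous to the concern under the single-nodule rule.

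With m the 12-month mean, the month-6 change has mean m/2 (placebo -0.1, aspirin -0.5). Two growth patterns set its SD, s:

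- Steady: month-6 change is half the month-12 change, so s = 1.6/2 = 0.80.
- Uneven: two independent half-year changes, so s = 1.6/√2 = 1.131.

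Proportion lost: P = 1 - Φ(z), with z = (2 - m/2)/s. 
Mean month-6 change of those lost: E6 = m/2 + s·φ(z)/P. 
Their mean month-12 change: E12 = 2·E6 (steady) or E6 + m/2 (uneven). 
Mean of those kept: (m - P·E12)/(1 - P).

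| Pattern, arm | z | P | Lost of 64 | E12 (mm) | Mean kept (mm) |
|---|---|---|---|---|---|
| Steady, placebo | 2.1/0.80 = 2.625 | 0.0043 | 0.28 | 4.50 | -0.220 |
| Steady, aspirin | 2.5/0.80 = 3.125 | 0.0009 | 0.06 | 4.44 | -1.005 |
| Uneven, placebo | 2.1/1.131 = 1.856 | 0.0317 | 2.03 | 2.34 | -0.283 |
| Uneven, aspirin | 2.5/1.131 = 2.210 | 0.0136 | 0.87 | 1.90 | -1.040 |

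Power from 40,000 simulated trials per case:

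| Share of progressors who leave | Lost of 128 | Difference (mm) | Power |
|---|---|---|---|
| none | 0 | 0.80 | 80% |
| all, steady | 0.3 | 0.78 | 79% |
| all, uneven | 2.9 | 0.76 | 77% |
| half, uneven | 1.4 | 0.78 | about 79% |
| a quarter, steady | 0.1 | 0.80 | 80% |
| a quarter, uneven | 0.7 | 0.79 | 79% |

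With no true effect (both means -0.2 mm), the rejection rate stayed close to 5% in every case. All these losses are below the imputation trigger of 5% × 128 = 6.4 participants, unless other missing CTs are added.

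**5. New lesions.** The normal model leaves these out. If one participant leaves with a single new 4 mm target lesion and other nodules unchanged, the arm mean moves by 4/64 = 0.06 mm, which is 0.0625/0.8 = 8% of the planned difference.

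**The case against.** The strongest reply is that this is an administrative list. Section 8.4 says participants may go off study, its list includes completing the intervention, and section 6.8 requires every consented participant to go off study formally at some point. Section 13.8 intends to assess everyone who took a dose. Section 13.9 says repeat CT is planned only at baseline and one year, so most progression will first be seen on the endpoint scan itself. In 6.9, progressive disease is only an example, and unblinding normally follows consultation with the NCI monitor. Section 8.4 does not define progression. It may mean a cancer or a nodule sent to biopsy, and if that nodule is removed there is no valid month-12 diameter whatever 8.4 says.

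Most of this stands, and it limits the size. It does not close the gap: intent is not a provision for a scan, and the off-study step in 6.9 carries no permissive wording once the blind is broken. Interim CT will also tend to fall on growing nodules. Appendix C, for example, sends progressing solid or partially solid nodules of 5-8 mm with doubling time under 400 days to CT after 3 months. The quarter-lost case is therefore an illustration, not a ceiling.

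A reader might infer more than the documents support, in four ways:

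- *That the plan requires progressors to leave.* It permits it.
- *That power falls to about 69% (difference 0.64 mm).* That figure comes from removing everyone whose month-12 change is at least 2 mm (8.5% on placebo, 3.0% on aspirin). Growth first seen at month 12 is seen on the endpoint scan, so no data are lost.
- *That a lower threshold applies generally.* Growth of 1.6 mm is 20% of two nodules at the 4 mm minimum (20% × 8 mm), on the reading that the 2 mm minimum does not carry over to multiple lesions. Applied to everyone, with all progressors leaving, it gives 0.73 to 0.75 mm and 74% to 78% power, but it does not describe the whole trial population. A 1 mm threshold is not in the plan.
- *That false positives increase.* With no true effect, both arms lose the same kind of participant.

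**Conclusion.** The gap is real: 8.4 and 6.9 allow a participant to leave because of growth in the quantity that the primary endpoint measures, and nothing secures the scan. The bias would be toward no effect. Its size cannot be known from the documents, which do not say how many participants will have an early CT or how many with progression would leave. At the 2 mm minimum, under the month-6 assumptions above, the cost is at most about 0.04 mm and 3 percentage points of power, and about 1 point or less if a quarter of progressors leave. New lesions, or CTs outside the schedule after month 6, could add to this. The effect is probably small. The change is still worth making, because it is cheap and a scan not done cannot be recovered.

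**What to change.** 1. **Section 8.4:** delete disease progression from the off-study reasons and state that it is not by itself a reason to go off study. This also stops the same exit under physician decision or other reason.
2. **Section 8.3:** add disease progression to the off-agent reasons, and say that these participants stay on study and have the planned month-12 CT if possible.
3. **Section 6.9:** for every unblinding, replace the off-study step with off agent, and say that follow-up and the month-12 CT continue unless consent is withdrawn. Limiting this to progression would leave the same loss after unblinding for other reasons, such as toxicity.

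The cost is a wording amendment and a little follow-up effort for participants who are off agent. No CT is added beyond the month-12 CT already planned, and the sample size does not change. How to count a nodule resected before month 12 still has to be settled separately.
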